4.4 FOLLOW-UP PERIOD

Duration of Follow Up

- An End of Treatment (EOT) visit will be conducted 30 (\pm 3) days after the last treatment visit (i.e., after last dose of leronlimab (PRO 140) and carboplatin).
- All patients will be followed for adverse events for 30 days after last dose of leronlimab (PRO 140) and Carboplatin, or until the patient starts a new treatment, whichever occurs first.
- Subjects who discontinue treatment for unacceptable adverse event(s) will be followed until resolution or stabilization of the adverse event (i.e. the grade is not changing).
- If a subject stops treatment due to unacceptable adverse event(s) but has not demonstrated disease progression, then the subject will be followed with imaging studies every 9 weeks until the time of progression radiographically according to RECIST v1.1 criteria. In the event that a radiographic response is detected, then this event will be included as a response in the final analysis, and the time of progression used in calculation of the survival analysis.
- Subjects will be followed up by clinic visits or phone call or another method of contact, for survival status every 3 months (\pm 1 month) for 2 years after treatment discontinuation or until death, whichever occurs first.

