4.4.2. Survival Follow-up Visits

Survival follow-up visits will be performed every 3 months (± 1 month) for 2 years after treatment discontinuation or until death, whichever occurs first. Subjects will be followed up by clinic visits or phone call or another method of contact, for survival status. During the visit, the following assessments will be performed:

- Survival status
- Concomitant medications (limited to all subsequent anti-cancer treatments)
- Toxicity assessment

Note: Subjects who discontinue treatment for unacceptable adverse event(s) will be followed until resolution or stabilization of the adverse event (i.e. the grade is not changing).

- Tumor imaging assessment (see [Section 7.15](#) and note below)

Note: If a subject stops treatment due to unacceptable adverse event(s) but has not demonstrated disease progression, then the subject will be followed with imaging studies every 9 weeks until the time of progression radiographically according to RECIST v1.1 criteria. In the event that a radiographic response is detected, then this event will be included as a response in the final analysis, and the time of progression used in calculation of the survival analysis.

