7.5.2. Prohibited Medications

Subjects are prohibited from receiving the following therapies during the Screening and Treatment Period of this trial:

- Anti-cancer systemic chemotherapy or biological therapy not specified in this protocol
- Investigational agents other than leronlimab (PRO 140)
- Radiation therapy

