7.15.6. Evaluation of Best Overall Response

The best overall response is the best response recorded from start of treatment until disease progression/recurrence (taking as reference for progressive disease the smallest measurements recorded since the start of treatment). The patient's best response assignment will depend on the achievement of both measurement and confirmation criteria. Responses will be assessed using CT scans or magnetic resonance imaging according to standard RECIST v1.1 criteria in order to assess disease progression. These criteria will also allow for patients who experience an initial disease

flare, and as some patients who will have a delayed response may experience an initial disease flare, these patients will be allowed to continue receiving study treatment beyond progression.

The following table provides overall responses for all possible combinations of tumor responses in target and non-target lesions with or without the appearance of new lesions:

Table 7-5: Time point response: subjects with target (\pm non-target) disease

Target lesions	Non-target lesions	New lesions	Overall response
CR	CR	No	CR
CR	Non-CR/non-PD	No	PR
CR	Not evaluated	No	PR
PR	Non-PD or not all evaluated	No	PR
SD	Non-PD or not all evaluated	No	SD
Not all evaluated	Non-PD	No	NE
PD	Any	Yes or No	PD
Any	PD	Yes or No	PD
Any	Any	Yes	PD

CR = complete response, PR = partial response, SD = stable disease, PD = progressive disease, and NE = inevaluable.

Note: To be assigned a status of PR or CR, changes in tumor measurements must be confirmed by repeat assessments that should be performed 6 weeks after the criteria for response are first met. In the case of SD, measurements must have met the SD criteria at least once after study entry at a minimum interval of 6 weeks.

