8.2 Analysis Primary Outcome Measure

8.2.1 Maximum Tolerated Dose (MTD) by evaluation of dose-limiting toxicities (DLTs) of leronlimab (PRO 140) when combined with carboplatin AUC5

The MTD will be summarized descriptively. The proportion of subjects at the different MTD levels and those who were able to tolerate the highest dose of leronlimab will be summarized descriptively.

8.2.2 Progression free survival (PFS) defined as time in months from the date of first study treatment to the date of disease progression or death from any cause, whichever comes first.

PFS will be calculated from the date of initial dose to the date of objective disease progression or death due to any cause, whichever occurs earlier. If patients discontinued treatment due to toxicity, withdrew consent without disease progression or death, PFS will be censored at the date of the last evaluable tumor assessment. A patient with no evaluable tumor assessments or who drop out before first follow-up period will be censored at the date of informed consent. If two or more consecutively scheduled tumor assessments have no data (not evaluable due to incomplete assessment, not assessed, or missing) and are followed by a PD assessment or death, the PFS will be censored at the last evaluable tumor assessment date prior to the assessments with no data. Patients will be explicitly censored for PFS at last adequate tumor assessment prior to initiation of new anticancer treatment or radiation.

Patients who are off-treatment without objective PD and getting the subsequent new anticancer therapy before the data cut-off then PFS will be censored at the last adequate tumor assessment before the new anticancer treatment start, regardless of whether there was a PD or death after the start of the new anticancer treatment.

Progression free survival (PFS) will be estimated using Kaplan-Meier curves, and the median PFS will be read from this curve.

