8.3 Analysis of Secondary Outcome Measures

8.3.1 PFS according to RECIST v1.1 in participants with Detectable Programmed Death-Ligand 1 (PD-L1)

PFS according to RECIST v1.1 in participants with Detectable Programmed Death-Ligand 1 (PD-L1) will be calculated using Kaplan-Meier curves, and the median PFS will be read from this curve. Note: The PD-L1 expression testing will be performed at baseline. Breast tissue (primary or metastatic site) collected to analyze for the presence of CCR5 at pre-screening will additionally be used for evaluating PD-L1 expression levels.

8.3.2 Overall response rate (ORR) and clinical benefit rate (CBR) in subjects with CCR5+ mTNBC treated with leronlimab (PRO 140) and carboplatin

Overall response rate (ORR) and clinical benefit rate (CBR) in subjects with CCR5+ mTNBC treated with leronlimab (PRO 140) and carboplatin will be calculated using proportions and 95% confidence intervals.

Note: Overall response rate defined as the proportion of patients who achieve an overall response of complete response or partial response in the total number of evaluable patients, assessed by RECIST v1.1. Clinical benefit rate is defined as the proportion of patients who achieve an overall response of complete response or partial response or stable disease in the total number of evaluable patients, assessed by RECIST v1.1. Imaging scans to be done at the end of 2 cycles (i.e., every 6 weeks) for the first 6 cycles (18 weeks) and at the end of 3 cycles (i.e., every 9 weeks) thereafter.

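### Responses first seen after a toxicity stop count towards ORR with no cut-off at new anticancer therapy, so a next-line response could be counted as a study response

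*Protocol*

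**What the plan says.** **Follow-up after a toxicity stop.** Under Protocol 4.4, for a patient who stops for unacceptable adverse events without progression, "the subject will be followed with imaging studies every 9 weeks until the time of progression radiographically". It continues: "In the event that a radiographic response is detected, then this event will be included as a response in the final analysis". The same rule is in Protocol 4.4.2, Protocol Table 4-1 footnote 23 and SAP Appendix 1 footnote 22. None of the four places mentions new therapy.

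**Response window.** Protocol 7.15.6: "The best overall response is the best response recorded from start of treatment until disease progression/recurrence". SAP 8.3.2 says that ORR and CBR "will be calculated using proportions and 95% confidence intervals", among evaluable patients, a term left undefined. Neither refers to new therapy.

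**New therapy in follow-up.** Protocol 7.5.2 limits its ban in time: "Subjects are prohibited from receiving the following therapies during the Screening and Treatment Period of this trial". Protocol 4.4.2 lists subsequent anticancer treatments among the items recorded at survival follow-up visits, next to tumor imaging.

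**Where a cut-off does exist.** SAP 8.2.2: "Patients will be explicitly censored for PFS at last adequate tumor assessment prior to initiation of new anticancer treatment or radiation". Protocol 4.4 also ends adverse-event follow-up at 30 days "or until the patient starts a new treatment, whichever occurs first".

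**The concern.** ORR and CBR are named Phase II secondary objectives. In a single-arm trial there is no control group, so every counted response is read as activity of the combination. A response that arises under the next regimen can only raise ORR, and SAP 7.4 plans no sensitivity analysis that would show it.

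The plan also becomes inconsistent within one patient. Suppose she stops for toxicity with stable disease, starts another regimen before progressing, and then has a confirmed partial response on the 9-weekly scans. Under the new-therapy rule of SAP 8.2.2 her PFS is censored before the new drug. Under Protocol 4.4 she is a responder because of a scan taken on it.

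**Working it through.** **No stated figure to reproduce.** Phase II has 30 patients by clinical judgment, with no power calculation (SAP 3), no formal hypothesis test (SAP 5) and no target ORR. The check is a reading of the rules, followed by a sizing on declared assumptions.

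**Step 1: does any rule stop the count at new therapy?**

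| Rule | Ends at progression | Ends at new therapy |
|---|---|---|
| Imaging and response after a toxicity stop (Protocol 4.4, 4.4.2, Table 4-1 fn 23; SAP Appendix 1 fn 22) | Yes | No |
| Best overall response (Protocol 7.15.6) | Yes | No |
| ORR/CBR (SAP 8.3.2) | Not stated | No |
| Adverse-event follow-up (Protocol 4.4) | Not applicable | Yes |
| PFS (SAP 8.2.2) | Event | Yes, censored |

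Responses to a next line that starts after progression are already excluded by Protocol 7.15.6. The gap is confined to therapy started before progression.

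**Step 2: size per case.** With all 30 evaluable, one such response adds 1/30 = 3.3 points. The step is larger if fewer are evaluable.

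**Step 3: expected excess.** Expected extra responders = (patients who stop for toxicity, have no progression or earlier response, and start a next line before progressing) × (next-line response rate). Both inputs are assumptions.

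- Low: 3 × 0.20 = 0.6 responders; 0.6/30 = +2.0 points. Chance of none: 0.8³ = 51%.
- High: 6 × 0.40 = 2.4 responders; 2.4/30 = +8.0 points. Chance of none: 0.6⁶ = 5%.

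A wider set of assumptions takes 3 to 9 toxicity stops, 50-100% of them switching before progression, and a 10-30% response rate:

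- Low: 3 × 0.5 × 0.10 = 0.15 responders, +0.5 points; chance of at least one 1 − 0.95³ = 14%.
- Middle: 6 × 1.0 × 0.20 = 1.2 responders, +4.0 points; chance of at least one 1 − 0.8⁶ = 74%.
- High: 9 × 1.0 × 0.30 = 2.7 responders, +9.0 points; chance of at least one 1 − 0.7⁹ = 96%.

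**Step 4: what two cases would look like.** With assumed counts and exact (Clopper-Pearson) 95% intervals, 9/30 = 30.0% (14.7 to 49.4) becomes 11/30 = 36.7% (19.9 to 56.1). The shift is well inside the sampling error, but it always goes in the same direction.

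**Step 5: CBR.** CBR counts CR, PR and SD. A patient who met the stable-disease criterion (at least 6 weeks after entry, Protocol 7.15.6) before switching already counts, so a later PR changes nothing. CBR rises only if stable disease or better is first documented under the new therapy.

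**Step 6: the rest of the anchor sentence.** It goes on to say that the progression date found in this follow-up enters the survival analysis. SAP 8.2.2 censors patients who discontinue for toxicity at their last evaluable tumor assessment. Unless its qualifier about absence of progression or death is meant to cover progression found later in follow-up, the two passages treat the same patient as an event and as censored.

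**The case against.** The strongest reply is that the rule has a sensible purpose. Protocol 7.15.6 anticipates delayed responses, and a response that appears off treatment before any other drug is fairly credited to the combination. The text does not tell anyone to count next-line responses; it is silent on them. That purpose stands, and the fix keeps those responses. But an inclusion rule written without a condition, applied as written, takes in next-line responses too. The confirmation requirement does not help: it tests whether a response persists, not which drug produced it.

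Three stronger readings are tempting and are not supported:

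- A reader might infer that next-line responses will in fact be credited, or that the protocol expects these patients to switch early. The record of subsequent treatments covers everyone in survival follow-up, including patients who progressed, and the adverse-event cut-off covers all patients. The documents permit the scenario; they do not predict it. The note to Protocol Table 6-4 also lets patients who discontinue carboplatin continue leronlimab. If they are then still in the Treatment Period, other anticancer therapy remains prohibited, so the affected group may be small.
- A reader might infer that CBR is inflated in the same way as ORR. Step 5 shows that it is not.
- A reader might infer that the primary result is biased by the same gap. PFS has its own new-therapy rule. The progression-date conflict in step 6 is a separate matter.

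It is also fair to say that ORR and CBR are secondary, that SAP 5 calls the study hypothesis generating, and that no ORR threshold drives a decision. This limits the weight of the point without supplying the missing cut-off.

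**Conclusion.** The point holds as a conditional defect in the response rule. Followed exactly, the plan counts a response to a new therapy as a study response when the patient stopped for toxicity, had not progressed, and then switched and responded. The size is 3.3 ORR points per case with 30 evaluable. The expected excess is 0.6 to 2.4 responders (+2 to +8 points) if 3 to 6 patients follow this path and 20-40% of them respond; under the wider assumptions it is +0.5 to +9.0 points. No frequency is given in the documents, and the realised excess may be zero. The textual gap is certain; its consequence is not. It should be corrected because the correction is cheap and ORR has no comparator, but it does not touch the new-therapy rule for PFS.

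**What to change.** In Protocol 4.4, 4.4.2, 7.15.6 and Table 4-1 footnote 23, and in SAP 8.3.2 and Appendix 1 footnote 22, add one rule: *best overall response, ORR and CBR use only tumor assessments up to the earlier of progression or the start of new anticancer treatment or radiation.* The terms should be those of SAP 8.2.2, so that response and PFS share one cut-off. State that off-treatment responses before that date still count, and that responses first met before the switch but not yet confirmed are reported separately.

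In the same edit, reconcile the use of the follow-up progression date in the anchor sentence with the censoring of toxicity discontinuations in SAP 8.2.2, and define evaluable for the ORR/CBR denominator.

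The cost is wording only. Subsequent anticancer treatments are already recorded (Protocol 4.4.2), and start dates are collected for medications and non-study treatments (Protocol 7.5). There are two downsides. ORR may come out slightly lower. A genuine response first seen just before a switch may stay unconfirmed, the more so because confirmation is due at 6 weeks while follow-up scans are 9 weeks apart; separate reporting keeps such cases visible. The rule should be settled before database lock, so that nobody decides which responses count after seeing them.

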4.4.1. End of Treatment Visit (EOT)

An EOT visit will take place 30 (\pm 3) days from the last treatment visit.

The following assessments will be performed at the EOT visit:

- Concomitant medications assessment (see [Section 7.5](#)),
- Review of Adverse Events (see [Section 9](#))
- Vital Signs (see [Section 7.6](#)),
- Physical examination, including evaluation of all body systems (see [Section 7.7](#)),
- ECOG Performance Status (see [Section 7.8](#)),

- 12-lead Electrocardiogram (see [Section 7.9](#)),
- Toxicity Assessment (see [Section 7.10](#)),
- Collection of lab specimens (see [Section 7.11](#)) for
 - Complete blood count
 - Biochemistry
 - Urine sample for urinalysis parameters
 - CTCs PD-L1/CCR5 Analysis
 - CTC and CAMLs Analysis
- Survival status (see [Section 7.16](#))

4.4.2. Survival Follow-up Visits

Survival follow-up visits will be performed every 3 months (± 1 month) for 2 years after treatment discontinuation or until death, whichever occurs first. Subjects will be followed up by clinic visits or phone call or another method of contact, for survival status. During the visit, the following assessments will be performed:

- Survival status
- Concomitant medications (limited to all subsequent anti-cancer treatments)
- Toxicity assessment

Note: Subjects who discontinue treatment for unacceptable adverse event(s) will be followed until resolution or stabilization of the adverse event (i.e. the grade is not changing).

- Tumor imaging assessment (see [Section 7.15](#) and note below)

Note: If a subject stops treatment due to unacceptable adverse event(s) but has not demonstrated disease progression, then the subject will be followed with imaging studies every 9 weeks until the time of progression radiographically according to RECIST v1.1 criteria. In the event that a radiographic response is detected, then this event will be included as a response in the final analysis, and the time of progression used in calculation of the survival analysis.

4.5 UNSCHEDULED VISITS

In the event that the subject will return to clinic at a time other than a regularly scheduled study visit, the visit will be regarded as an unscheduled visit. Assessments at unscheduled visits are at

the discretion of the Investigator. All pertinent findings, including adverse events or changes in medications, will be noted in the eCRF.

Any hospitalization or ER visits in between the scheduled visits should be promptly notified to the site staff.

5 SUBJECT COMPLETION, WITHDRAWAL AND CRITERIA FOR STOPPING THE STUDY

A subject is considered to have completed the study once all survival follow-up visit assessments up to 2 years after treatment discontinuation have been performed or until death, whichever occurs first.

While subjects are encouraged to complete all study evaluations, they may withdraw from the study at any time and for any reason. Reasonable effort will be made to determine why any subject withdraws from the study prematurely. This information will be recorded. If a subject withdraws prematurely after dosing, subjects will be monitored until they are stable for discharge from the clinic. All data normally collected at the scheduled Post-Study (Follow-up) Visit should be recorded at the time of premature discontinuation.

5.1 REMOVAL OF SUBJECTS FROM STUDY TREATMENT AND/OR STUDY AS A WHOLE

Subjects can be taken off the study treatment and/or study as a whole at any time at their own request, or they may be withdrawn at the discretion of the investigator for safety, behavioral or administrative reasons. The reason(s) for discontinuation must be clearly documented on the appropriate eCRF and may include:

- Subject voluntarily withdraws from treatment (follow-up permitted)
- Subject withdraws consent (no follow-up permitted)
- Subject is unable to comply with protocol requirements
- Subject demonstrates disease progression
- Subject experiences unacceptable toxicity
- Treating physician determines that continuation on the study would not be in the subject's best interest
- Subject becomes pregnant
- Subject develops a second malignancy that requires treatment which would interfere with this study
- Subject becomes lost to follow-up (LTf)

If a subject fails to return for the scheduled study visit or is discontinued from the study, an attempt will be made to determine the reason(s). If the subject is unreachable by telephone, a registered letter will be sent to the subject requesting that he/she contact the clinic.

All patients with an ongoing SAE at the Post-Study (Follow-up) Visit (scheduled or premature) must be followed until the event is resolved (with or without sequelae) or deemed stable.

5.2 SUBJECT REPLACEMENT

Three subjects within a dose level must be observed for one cycle (21 days) before accrual to the next higher dose level may begin. If a subject is withdrawn from the study prior to completing one cycle of therapy without experiencing a DLT prior to withdrawal, an additional subject may be added to that dose level.

Subjects missing leronlimab (PRO 140) administration (during the DLT period i.e., Cycle 1) due to toxicity will not be replaced since these subjects will be considered to have experienced a dose limiting toxicity.

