- If two or more subjects out of the six subjects treated at this dose exhibit a DLT, the dose escalation stops at that level and the next lower dose is considered as the MTD. When the escalation has stopped, additional subjects will be treated at the MTD to a total of six subjects.

A schematic of the “3 + 3” Dose Escalation Study Design is provided in [Figure 3-2](#).

Cohorts of 3 patients are entered at given dose level K. If no patients have a DLT, then the dose will be escalated to the next dose level, K +1. If more than 1 subject has a DLT then the previous dose level, K -1, will be considered as MTD. If 1 subject has a DLT an additional 3 patients will be treated at this dose level, K. If no further subjects suffer a DLT then the dose level will be escalated to K +1 and if any further subjects have a DLT then the previous dose level, K -1, will be considered the MTD. The MTD will be the maximum dose level with an observed toxicity rate of 0% or 17%.

Figure 3-2: 3+3 Study Design

Note: A standard “3 +3” dose escalation design starting at dose \mathcal{K} . The maximum tolerated dose (MTD) is the highest dose at which 0 or 1 dose-limiting toxicities (DLTs) are observed in six subjects. If de-escalation occurs at the first dose level, the study is discontinued.

Cohort escalation (i.e., the decision to progress from one cohort (dose level) to another) will not proceed until all of the following four events have occurred:

- (1) All study subjects in a given cohort (dose level) have been enrolled, and
- (2) All such subjects have been followed for at least 3 weeks (Cycle 1) after the first injection, and
- (3) The Sponsor’s Medical Monitor has reviewed the available safety data (and has had the opportunity to discuss the data with the CRO’s Medical Monitor and PI, if necessary), and recommends further dose escalation and
- (4) The PI has determined that none of the SAEs or DLTs outlined below has occurred.
 - a. Death in any subject in which the cause of death is judged to be possibly, probably or definitely related to leronlimab (PRO 140)

- b. The occurrence in any subject of an anaphylactic reaction to leronlimab (PRO 140)
- c. The occurrence in any subject of a severe local injection site reaction (Grade 3 which is not resolved or recurs; or Grade 4) that precludes administration of consecutive leronlimab (PRO 140) doses.

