- d. The occurrence in any subject of a life-threatening SAE whose causal relationship to leronlimab (PRO 140) is judged to be probable or definite
- e. The occurrence of one or more non-life-threatening SAEs whose causal relationship to leronlimab (PRO 140) is judged to be definite
- f. The occurrence, in one or more subjects, of Grade 4 laboratory abnormalities, judged to be probably or definitely related to receipt of leronlimab (PRO 140)
- g. The occurrence of hematologic and non-hematological adverse events, judged to be possibly, probably or definitely related to receipt of leronlimab (PRO 140) based on previous clinical experience and that are of CTCAE Grade 3 or greater severity. Permissible exceptions to this rule include Grade 3 fatigue of less than one week duration, and Grade 3 nausea, vomiting, and diarrhea that resolve within 48 hours following institution of appropriate supportive care.
- h. Hy's law
- i. Neutropenic fever
- j. Grade 4+ neutropenia or thrombocytopenia >7 days
- k. Grade 3+ thrombocytopenia with bleeding
- l. Grade 3+ electrolyte abnormality that lasts >72 hours, unless the patient has clinical symptoms, in which case all grade 3+ electrolyte abnormality regardless of duration should count as a DLT. Grade 3+ amylase or lipase elevation NOT associated with symptoms or clinical manifestations of pancreatitis does not need to be counted as a DLT
- m. For patients with hepatic metastases, AST or ALT >8xULN or AST or ALT >5x ULN for ≥ 14 days

If any of the SAEs or DLTs outlined above have occurred, the Data Safety Monitoring Board (DSMB) will conduct an independent review of the data and make a final decision for dose escalation to the next cohort.

The dosing regimen for each cohort is as follows:

- Cohort A: 350 mg leronlimab (PRO 140) SC weekly + AUC 5 Carboplatin every 3 weeks
- Cohort B: 525 mg leronlimab (PRO 140) SC weekly + AUC 5 Carboplatin every 3 weeks
- Cohort C: 700 mg leronlimab (PRO 140) SC weekly + AUC 5 Carboplatin every 3 weeks

Leronlimab (PRO 140) is administered as subcutaneous injection in the abdomen weekly. A total of 350 mg, 525 mg, or 700 mg (175 mg/mL) is delivered as two injections on opposite sides of the abdomen. The 350 mg dose will be delivered as two injections of 1 mL each, 525 mg dose will be delivered as two injections of 1.5 mL each and 700 mg dose will be delivered as two injections of 2 mL each.

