6.1.5. Leronlimab (PRO 140) - Dose Modifications

The dose interruption, reduction, and permanent discontinuation for any toxicity are described below.

Dose interruption: Refer to [Table 6-3](#) below. Recovery to acceptable levels must occur to allow leronlimab (PRO 140) continuation. Any adverse event deemed to be related to leronlimab (PRO 140) that requires a dose hold of more than 21 days will result in permanent discontinuation of leronlimab (PRO 140).

Table 6-3: Leronlimab (PRO 140) Dose Modification and Management for Injection Site Reactions

CTCAE Grade	Treatment Modifications
Grade 1	No dose adjustment is required.
Grade 2	First Occurrence: No dose adjustment is required. Second Occurrence of the same event: Closely follow-up for resolution of the AE to Grade ≤ 1
Grade 3	Withhold treatment until symptoms resolve to: • Grade 1 or less
Grade 4	Study treatment will be permanently discontinued
Dose Limiting Toxicities (DLT) as outlined under Section 3 (Study Design)	Study treatment will be permanently discontinued

Note:

- *If Grade 3 event meets the DLT criteria: Study treatment will be permanently discontinued*
- *If Grade 3 event does not meet the DLT criteria: Study treatment will be withheld until symptoms resolve to Grade 1 or less before administering the next dose.*

Dose Modification: If a dose-response relationship for toxicity is observed, a reduced dose can be given to the subject. Dose adjustments will be allowed based on the toxicity, efficacy evaluation, and clinical judgment by physician.

- **Cohort B (PRO 140 525 mg):**

Dose de-escalation: If a dose-response relationship for toxicity is observed at leronlimab (PRO 140) 525 mg dose, the dose can be de-escalated to 350 mg. If no toxicity is observed at reduced dose (350 mg), the subjects will receive the reduced dose until disease progression, consent withdraw or death. No more dose de-escalation will be allowed if another toxicity event is observed at reduced dose level.

- **Cohort C (PRO 140 700 mg):**

Dose de-escalation: If a dose-response relationship for toxicity is observed at leronlimab (PRO 140) 700 mg dose, the dose can be de-escalated to 525 mg. If no toxicity is observed at reduced dose (525 mg), the subjects will receive the reduced dose until disease progression, consent withdraw or death. One more dose de-escalation (to 350 mg) will be allowed as per discretion of the treating physician.

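### Section 5.2 makes a Cycle 1 leronlimab dose missed for toxicity a DLT, but the DLT list and Table 6-3 do not, so a narrow group of subjects has two DLT statuses

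*Protocol*

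**What the plan says.** Protocol Section 5.2 deals with replacement of Phase Ib subjects. Those who miss leronlimab in Cycle 1 "due to toxicity will not be replaced since these subjects will be considered to have experienced a dose limiting toxicity". No grade, attribution or duration is required.

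The DLT criteria themselves are the list a–m in Protocol Section 3, repeated in the synopsis, Sections 8.5 and 12, and SAP Section 4. No copy has an item for a missed dose. Two items matter here:

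- Item c covers a severe injection site reaction: "Grade 3 which is not resolved or recurs; or Grade 4) that precludes administration of consecutive leronlimab (PRO 140) doses".
- Item g covers Grade 3 or higher events at least possibly related to leronlimab, with exceptions: "Permissible exceptions to this rule include Grade 3 fatigue of less than one week duration", and Grade 3 nausea, vomiting or diarrhea that settles within 48 hours of supportive care.

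Section 6.1.5 opens broadly: "The dose interruption, reduction, and permanent discontinuation for any toxicity are described below". Table 6-3 is nevertheless titled for injection site reactions. Its DLT row, which calls for permanent discontinuation, applies to "Dose Limiting Toxicities (DLT) as outlined under Section 3 (Study Design"). The note below the table splits Grade 3 events in two. On one side: "If Grade 3 event meets the DLT criteria: Study treatment will be permanently discontinued". On the other: "If Grade 3 event does not meet the DLT criteria: Study treatment will be withheld until symptoms resolve to Grade 1 or less". Section 9.2.6 also pauses leronlimab for a Grade 3 injection site reaction and lets the investigator restart it after recovery to Grade 1 or less.

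The SAP does not mention the Section 5.2 rule.

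**The concern.** The Phase Ib primary endpoint is the MTD, and it follows entirely from the number of subjects with a DLT. A protocol that states two different conditions for a DLT leaves that count open. Table 6-3 foresees a subject who has leronlimab withheld for toxicity and has not had a DLT. Section 5.2 makes the same subject a DLT once the withheld dose is a missed Cycle 1 dose.

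Three things then depend on which passage is applied: the 3+3 decision and so the Phase II dose; whether the event is one that sends the escalation decision to the DSMB; and whether the subject stops leronlimab or resumes it.

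**Working it through.** **1. The plan's own figures.** 1/6 = 16.7%, the stated 17%. 2/6 = 33.3%, which reaches the stated 33% boundary. Three levels × 6 subjects = 18, the stated Phase Ib maximum. All reproduce.

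**2. When the passages conflict.** Leronlimab is due on Days 1, 8 and 15 of Cycle 1. Table 4-1 allows ±1 day for the Day 8 and Day 15 visits, and the DLT period is the first 21 days. A conflict needs all three of these:

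- leronlimab is held for toxicity;
- recovery comes too late for the visit window, so the Day 8 or Day 15 dose is missed and not merely delayed;
- no item of a–m is met.

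Subjects who can satisfy all three:

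- A Grade 3 injection site reaction that is Grade 2 on the dosing day. The Table 6-3 note still requires the hold, and one missed dose need not preclude consecutive doses under item c. The example fails if item g is read to cover the reaction.
- A Grade 3 event excepted under item g, such as short fatigue, if Section 6.1.5 is read as covering any toxicity.
- A toxicity not attributed to leronlimab and outside items h–m. Section 5.2 does not ask for attribution.

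**3. The same subject under each reading.**

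| | Section 5.2 | Section 3 list with Table 6-3 |
|---|---|---|
| DLT in the 3+3 count | Yes | No |
| Listed event that triggers DSMB review | Not addressed | No |
| Leronlimab afterwards | Discontinue, if DLT status carries over to Section 6.1.5 | Withhold, then resume |

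The carry-over in the last row is not settled by the text. The DLT row of Table 6-3 points to Section 3, but the closing line of Section 6.1.5, on discontinuation for a DLT at 350 mg, does not.

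**4. Effect of one subject on the 3+3 rule.** 0/3 (escalate) becomes 1/3 (expand). 1/6 = 17% (escalate, or acceptable as MTD) becomes 2/6 = 33% (stop; the next lower level is the MTD).

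**5. How often.** Let q be the probability that a subject misses a Cycle 1 dose for toxicity without meeting a–m. The documents give no value, so 5%, 10% and 20% are assumed, with subjects independent.

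At least one of three affected: 1 − (1 − q)³.

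Escalation past a level on these events alone requires 0/3, or 1/3 followed by 0/3: E(q) = (1 − q)³ + 3q(1 − q)² × (1 − q)³. Stopping is 1 − E(q).

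| q | At least 1 of 3 | E(q) | Stop at the level |
|---|---|---|---|
| 5% | 1 − 0.857 = 14% | 0.857 + 0.116 = 0.973 | 2.7% |
| 10% | 1 − 0.729 = 27% | 0.729 + 0.177 = 0.906 | 9.4% |
| 20% | 1 − 0.512 = 49% | 0.512 + 0.197 = 0.709 | 29% |

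**6. On top of a–m DLTs.** Let p be the a–m DLT rate, also assumed. Counting both kinds of event gives E(p + q). With p = 10%, the chance of escalating past a level is 0.906 on a–m alone. It is 0.814, 0.709 or 0.494 when missed doses at q = 5%, 10% or 20% are added.

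**The case against.** The strongest reply is that little is left after items c and g. Item c is itself about precluded doses, and item g makes most Grade 3 events related to leronlimab DLTs already. Item g's exceptions are short-lived and will often clear before the next weekly dose. Section 1.4.3 reports no dose-limiting toxicities in earlier trials, although those were mostly in healthy or HIV-positive subjects. This stands as a limit on size: the group is narrow but not empty.

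The passages can also be harmonised, with Section 5.2 as a counting rule and Table 6-3 as a rule for the individual's treatment. That is a sensible reading, but neither document states it. It would still leave cohort counting and the DSMB trigger on different DLT definitions.

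Third, escalation is not left to one reader. Each cohort has a safety review, the medical monitors and investigators must be satisfied, and the DSMB reviews the data before the MTD is final. Section 5.2 can only add DLTs, so applying it moves decisions toward expanding or stopping. This lowers the risk of an unnoticed error, but does not tell the reviewers which count to use.

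A reader might infer more than the text supports in two ways:

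- That every held or delayed Cycle 1 dose creates the contradiction. Section 5.2 speaks of missed doses, and a hold that ends within the visit window is not one.
- That the binomial chance of at least two affected subjects in six (3%, 11% or 34% at the same assumed rates) is the chance of stopping. It is not, because a level with 0/3 escalates without first being expanded to six.

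**Conclusion.** The inconsistency is real and rests on the text, not on assumed rates. Section 5.2 contains a DLT condition that the governing list lacks, and Table 6-3 and Section 9.2.6 provide for holds that the list does not treat as DLTs. It affects only subjects who actually miss the Day 8 or Day 15 dose for toxicity without meeting a–m. For such a subject, one reclassification is enough to change an escalation decision or lower the MTD by a level.

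The probabilities illustrate scale only. They assume q between 5% and 20%, p = 10% where a–m DLTs are included, independent subjects, and no subject counted under both p and q. If q is well below 5%, the effect is correspondingly small. The documents do not support saying that Grade 3 holds in general have two statuses, or that reviewers would necessarily reach different decisions.

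**What to change.** The sponsor should reconcile Protocol Sections 3, 5.2, 6.1.5 with Table 6-3, 8.5, 9.2.6 and 12, and SAP Section 4, in one of two ways:

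- Let one DLT definition govern cohort counting, DSMB review and the DLT row of Table 6-3. Either the missed-dose condition is added to every copy of the list and the Table 6-3 note is aligned with it, or it is removed from Section 5.2.
- Keep both rules and state that Section 5.2 applies to cohort counting only. The text should then say whether such a count goes to the DSMB and that it does not invoke the Table 6-3 DLT row. SAP Section 4 should carry the same statement.

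Either way, the protocol should say when a held dose counts as missed and whether Table 6-3 covers injection site reactions only or any toxicity. This review does not say which clinical rule is right. The cost is protocol and SAP wording; no sample size, visit or data collection changes.
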